## List of abbreviations

AE	Adverse Event
ACE2	Angiotensin-converting enzyme 2
ALP	Alkaline Phosphatase
ALT	Alanine Aminotransferase
ANC	Absolute neutrophil count
ARDS	Acute respiratory distress syndrome
AST	Aspartate Aminotransferase
ASTCT	American society for transplantation and cellular therapy
██████	████████████████████
BUN	Blood Urea Nitrogen
CFR	Case fatality rate
CMO&PS	Chief Medical Office and Patient Safety
CoV	Coronaviruses
COVID-19	Coronavirus disease 2019
██████	████████████████████
CRF	Case Report/Record Form (paper or electronic)
CRP	C-reactive protein
CRS	Cytokine release syndrome
CT Scan	Computed tomography scan
DMC	Data Monitoring Committee
██████	████████████████████
ECG	Electrocardiogram
ECMO	Extracorporeal membrane oxygenation
EDC	Electronic Data Capture
EMA	European medicines agency
EOI	End of Infusion
FAS	Full analysis set
FDA	Food and Drug Administration
FiO 2	Fraction of inspired oxygen
GCP	Good Clinical Practice
GGT	Gamma-glutamyl transferase
hr	Hour
i.v./IV	intravenous
IB	Investigator's Brochure
ICF	Informed Consent Form
ICH	International Council for Harmonization of Technical Requirements for Pharmaceuticals for Human Use
ICU	Intensive care unit
IEC	Independent Ethics Committee
IL	Interleukin
IL-1R	IL-1 receptor

IN	Investigator Notification
IRB	Institutional Review Board
IRT	Interactive Response Technology
ITT	Intent to treat
LLOQ	lower limit of quantification
MedDRA	Medical dictionary for regulatory activities
mg	milligram(s)
mL	milliliter(s)
PaO 2	Partial pressure of oxygen
PBO	Placebo
PCR	Polymerase chain reaction
█	██████████
█	██████████
RRT	Renal replacement therapy
s.c.	subcutaneous
SAE	Serious Adverse Event
SAP	Statistical Analysis Plan
SARS-CoV-2	Severe Acute Respiratory Syndrome Coronavirus-2
SOC	Standard of care
SpO 2	Peripheral capillary oxygen saturation
SUSAR	Suspected Unexpected Serious Adverse Reaction
ULN	upper limit of normal
WHO	World Health Organization
WoC	Withdrawal of Consent

[figure not shown]

## Glossary of terms

Additional treatment	Medicinal products that may be used during the clinical trial as described in the protocol, but not as an investigational medicinal product (e.g. any background therapy)
Assessment	A procedure used to generate data required by the study
Biologic Samples	A biological specimen including, for example, blood (plasma, serum), saliva, tissue, urine, stool, etc. taken from a study participant
Cohort	A specific group of participants fulfilling certain criteria and generally treated at the same time
Control drug	A study drug (active or placebo) used as a comparator to reduce assessment bias, preserve blinding of investigational drug, assess internal study validity, and/or evaluate comparative effects of the investigational drug
Dosage	Dose of the study treatment given to the participant in a time unit (e.g. 100 mg once a day, 75 mg twice a day)
Electronic Data Capture (EDC)	Electronic data capture (EDC) is the electronic acquisition of clinical study data using data collection systems, such as Web-based applications, interactive voice response systems and clinical laboratory interfaces. EDC includes the use of Electronic Case Report Forms (eCRFs) which are used to capture data transcribed from paper source forms used at the point of care
End of the clinical trial	The end of the clinical trial is defined as the last visit of the last participant or at a later point in time as defined by the protocol
Enrollment	Point/time of participant entry into the study at which informed consent must be obtained
Estimand	A precise description of the treatment effect reflecting the clinical question posed by the trial objective. It summarizes at a population-level what the outcomes would be in the same patients under different treatment conditions being compared. Attributes of an estimand include the population, variable (or endpoint) and treatment of interest, as well as the specification of how the remaining intercurrent events are addressed and a population-level summary for the variable.
Healthy volunteer	A person with no known significant health problems who volunteers to be a study participant
Intercurrent events	Events occurring after treatment initiation that affect either the interpretation or the existence of the measurements associated with the clinical question of interest.
Investigational drug/ treatment	The drug whose properties are being tested in the study
Medication number	A unique identifier on the label of medication kits
Mis-randomized participants	Mis-randomized participants are those who were not qualified for randomization and who did not take study treatment, but have been inadvertently randomized into the study
Other treatment	Treatment that may be needed/allowed during the conduct of the study (i.e. concomitant or rescue therapy)
Part	A sub-division of a study used to evaluate specific objectives or contain different populations. For example, one study could contain a single dose part and a multiple dose part, or a part in participants with established disease and in those with newly-diagnosed disease
Participant	A trial participant (can be a healthy volunteer or a patient)
Participant number	A unique number assigned to each participant upon signing the informed consent. This number is the definitive, unique identifier for the participant and should be used to identify the participant throughout the study for all data collected, sample labels, etc.
Period	The subdivisions of the trial design (e.g. Screening, Treatment, Follow-up) which are described in the Protocol. Periods define the study phases and will be used in clinical trial database setup and eventually in analysis
Personal data	Participant information collected by the Investigator that is coded and transferred to Novartis for the purpose of the clinical trial. This data includes participant identifier information, study information and biological samples.

Premature participant withdrawal	Point/time when the participant exits from the study prior to the planned completion of all study drug administration and/or assessments; at this time all study drug administration is discontinued and no further assessments are planned
Randomization number	A unique identifier assigned to each randomized participant
Screen Failure	A participant who did not meet one or more criteria that were required for participation in the study
Source Data/Document	Source data refers to the initial record, document, or primary location from where data comes. The data source can be a database, a dataset, a spreadsheet or even hard-coded data.
Start of the clinical trial	The start of the clinical trial is defined as the signature of the informed consent by the first participant
Study treatment	Any drug or combination of drugs or intervention administered to the study participants as part of the required study procedures; includes investigational drug(s), control(s) or background therapy
Study treatment discontinuation	When the participant permanently stops taking any of the study drug(s) prior to the defined study treatment completion date (if any) for any reason; may or may not also be the point/time of study discontinuation
Treatment arm/group	A treatment arm/group defines the dose and regimen or the combination and may consist of 1 or more cohorts.
Treatment of interest	The treatment of interest and, as appropriate, the alternative treatment to which comparison will be made. These might be individual interventions, combinations of interventions administered concurrently, e.g. as add-on to standard of care, or might consist of an overall regimen involving a complex sequence of interventions. This is the treatment of interest used in describing the related clinical question of interest, which might or might not be the same as the study treatment.
Variable (or endpoint)	The variable (or endpoint) to be obtained for each participant that is required to address the clinical question. The specification of the variable might include whether the participant experiences an intercurrent event.
Withdrawal of study consent (WoC)	Withdrawal of consent from the study occurs only when a participant does not want to participate in the study any longer and does not allow any further collection of personal data

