### 9.1.2 Withdrawal of informed consent

Participants may voluntarily withdraw consent to participate in the study for any reason at any time. Withdrawal of consent (WoC) occurs only when a participant:

- Does not want to participate in the study anymore,  
and
- Does not want any further visits or assessments  
and
- Does not want any further study related contacts

In this situation, the investigator should make a reasonable effort (e.g. telephone, e-mail, letter) to understand the primary reason for the participant's decision to withdraw his/her consent and record this information.

Where consent to the use of personal and coded data is not required, participant therefore cannot withdraw consent. They still retain the right to object to the further use of personal data.

Study treatment must be discontinued and no further assessments conducted, and the data that would have been collected at subsequent visits will be considered missing.

Further attempts to contact the participant are not allowed unless safety findings require communicating or follow-up.

All efforts should be made to complete the assessments prior to study discontinuation. A final evaluation at the time of the participant's study discontinuation should be made as detailed in the assessment table.

Novartis will continue to retain and use all research results (data) that have already been collected for the study evaluation.

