### 2.6.1 Key secondary estimand

The key secondary clinical question of interest in this study is: Does the administration of canakinumab reduce 4-week mortality among patients with COVID-19-induced pneumonia and CRS, regardless of other subsequent clinical interventions?

The justification for this secondary estimand is that mortality currently represents the main epidemiological and clinical concern for COVID-19 patients and accumulating evidences suggest coexistence of CRS with severe COVID-19-induced pneumonia. Subsequent clinical interventions, including intensive care when a patient become terminally ill, reflect actual clinical practices, whose needs, scope and effectiveness could potentially be related to the earlier decision of canakinumab administration.

The key secondary estimand includes the following components:

Population: Hospitalized patients with COVID-19-induced pneumonia and CRS.

Endpoint: All COVID-19-related deaths (i.e., all deaths caused by study indication) during the 4-week period after study treatment

Treatment of interest: The randomized study treatment (canakinumab or placebo) added onto SOC with or without additional subsequent clinical interventions.

Handling of remaining intercurrent events:

The treatment policy strategy will be adopted for this key secondary analysis.

- Effect of other subsequent clinical interventions will not be adjusted
- Early study discontinuation or lost to follow-up before Day 29: a patient will be considered as survivor if the last clinical status of 0 or 1; otherwise, the patient will not be included in this key secondary analysis (note: this include deaths which are not marked as caused by study indication).

Summary measure: Odds-ratio comparing 4-week CFR in the canakinumab and control groups.

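### Withdrawal of consent is defined in two different ways, and neither text says whether ventilation and death may still be read from the hospital record when only visits and contact are refused

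*Protocol*

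**What the plan says.** **Two definitions.** The protocol glossary limits withdrawal of consent to a participant who "does not want to participate in the study any longer and does not allow any further collection of personal data". Its entry for personal data covers coded information transferred to the sponsor: "This data includes participant identifier information, study information and biological samples". Protocol 9.1.2 is also phrased as an only-when rule, but its three joint conditions are different. The participant wants no more participation, no more visits or assessments, and "Does not want any further study related contacts". Refusal of data collection is not among them. Personal data appear there only in a separate provision for cases where consent to data use is not required: "They still retain the right to object to the further use of personal data".

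**Consequence of withdrawal.** Protocol 9.1.2 continues with "no further assessments conducted, and the data that would have been collected at subsequent visits will be considered missing". Data gathered before that point are kept: "Novartis will continue to retain and use all research results (data) that have already been collected for the study evaluation". Protocol 9.1.1 keeps patients who stop treatment or participation in follow-up unless they withdraw consent, and refers the site to 9.1.2 for what that means.

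**Analysis rules for exit before Day 29.**
- Primary (Protocol 2.1, SAP 2.5.1): non-responder, unless the patient was not invasively ventilated from Day 3 and was either discharged at status 0 or 1, or last scored on Day 15 or later and better than baseline.
- Primary, exit before Day 3 (SAP 2.5.3): excluded.
- Key secondary (SAP 2.6.1): survivor if the last status was 0 or 1; "otherwise, the patient will not be included in this key secondary analysis".

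**The concern.** The primary endpoint is invasive ventilation or death from Day 3 to Day 29, and the key secondary is COVID-19-related death over four weeks. For an inpatient, ventilation and death are routinely charted and can be read without a study visit or a call. Whether a patient counts as withdrawn therefore decides whether an observable outcome is used or replaced by a rule.

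Take an inpatient on oxygen who, between Day 3 and Day 14, refuses study procedures and contact but says nothing against use of the record. Under the glossary this patient has not withdrawn consent. Under 9.1.2 the patient has. On the second reading none of the responder or survivor exceptions is met, so the patient becomes a non-responder in the confirmatory test and disappears from the mortality analysis, whatever the chart shows. Both estimands are labelled treatment policy, which calls for the observed outcome where it can lawfully be had. With two definitions in force, sites may classify such patients differently.

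**Working it through.** **Step 1. The texts side by side**

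| Condition | Glossary | Section 9.1.2 |
|---|---|---|
| No further participation | required | required |
| No further visits or assessments | not mentioned | required |
| No further study contacts | not mentioned | required |
| No further collection of personal data | required | not mentioned |

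Neither list contains the other, so the two texts classify the patient described above differently. The sentence on missing data speaks of subsequent visits; it neither permits nor forbids use of the hospital record.

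**Step 2. Reproduce the plan's power**

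Inputs: 450 patients randomised 1:1, so n = 225 per arm; two-sided 0.05; control response 20% to 50%; benefit 15 points (Protocol 12.7.1, Table 12-1). For the primary endpoint I used a Wald test on the log odds ratio:

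SE = sqrt{[1/(pc(1−pc)) + 1/(pt(1−pt))]/n}; power = Φ(ln OR/SE − 1.96).

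At 50% versus 65%: ln OR = 0.619, SE = 0.1932, ratio 3.205, power Φ(1.245) = 89.3%. The four rows of Table 12-1 give 89.3, 88.8, 90.5 and 94.2%, against 89, 89, 90 and 94% stated.

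For the key secondary I used the pooled-variance normal approximation:

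power = Φ{[|d| − 1.96·sqrt(2p̄(1−p̄)/n)] / sqrt[(pc(1−pc) + pt(1−pt))/n]}.

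This gives 92.7, 84.6 and 71.3%, against 92, 83 and 70% in Table 12-2. Both tables reproduce within 2 points.

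**Step 3. Upper bound on the effect**

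Let w be the share of an arm that withdraws in this way. The documents give no value, so 2% and 5% are assumptions. As the worst case, every such patient is scored a non-responder (observed rate p(1−w)) and is deleted from the fatality analysis (n becomes 225(1−w)).

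Primary endpoint, true rates 50% versus 65%:

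| w placebo / canakinumab | Observed rates | Difference (points) | ln OR / SE | Power |
|---|---|---|---|---|
| 0 / 0 | 50.0 vs 65.0% | 15.0 | 0.619/0.1932 | 89.3% |
| 2% / 2% (9 of 450) | 49.0 vs 63.7% | 14.7 | 0.602/0.1924 | 87.9% |
| 5% / 5% (22.5 of 450) | 47.5 vs 61.75% | 14.25 | 0.579/0.1914 | 85.7% |
| 2% / 4% | 49.0 vs 62.4% | 13.4 | 0.547/0.1916 | 81.4% |

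With no true effect and 50% response in both arms, the 2% / 4% split gives 0.50 × 0.96 − 0.50 × 0.98 = −1.0 point.

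Key secondary: w = 2% leaves 225 × 0.98 = 220.5 per arm, and power moves from 92.7, 84.6 and 71.3% to 92.2, 83.9 and 70.4%.

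**The case against.** **The group may be almost empty.** The glossary defines an assessment as any procedure that generates data the study requires, and Protocol 8.3.1 makes the daily score a review of the previous day's status. Refusing all assessments can thus be read as refusing the score itself. This has force, but it depends on combining three passages that a site may not combine. On that reading, 9.1.2 would also close off the record for a patient who never objected to its use.

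**A reader might infer that the plan throws away chart outcomes.** The documents do not say so. Section 9.1.2 is silent on charts and vital status, keeps what was already collected and asks for a final evaluation; Protocol section 3 moves the Day 29 assessments to the day of discontinuation. What stands is the absence of a rule for outcomes after that day.

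**A reader might also infer that every such withdrawal is scored as failure or deleted.** That is too strong. There are two responder routes, a survivor rule and an exclusion before Day 3. The fatality omissions are bracketed: Protocol 12.5.1 counts all early exits as survivors, and SAP 2.6.5 counts them as non-survivors. These analyses change the imputation; they do not recover the true outcome.

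**The rate has no anchor.** The plan expects early discontinuation before recovery to be unlikely (12.7.1) and loss to follow-up before recovery to be minimal (12.7.2). No mechanism for unequal withdrawal is stated in this double-blind, single-infusion trial. I accept this: the figures above are bounds, not forecasts.

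**Adding refusal of data collection as a compulsory fourth condition in 9.1.2 would be a poor remedy.** It would make withdrawal harder and sits badly with the right to withdraw for any reason at any time and to object to data use. The consent form is not in the public text, so what it permits cannot be checked. This objection is right, and the fix respects it.

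**Conclusion.** The definitions conflict and should be reconciled. For a patient who refuses visits and contact but not data collection, the plan does not settle whether consent has been withdrawn or whether ventilation and vital status may be taken from the record. The analysis consequence is limited to exits from Day 3 to before Day 29 that meet no responder or survivor exception, plus the omission from the fatality analysis of earlier exits whose last status was above 1.

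The size is probably small. Under the worst-case scoring, an assumed 2% in both arms costs about 1.4 points of power at 50% versus 65% (89.3% to 87.9%). Unequal rates matter more, because they shift the estimate itself: an assumed 2% versus 4% moves a null difference by 1.0 point. These results rest on assumed rates and on ignoring the exceptions. A reader might take them to show that the trial was underpowered or that Tables 12-1 and 12-2 are wrong; they do not, since both tables reproduce.

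This is a cheap improvement in data capture and consistency. It is not evidence that the primary test is invalid.

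**What to change.** 1. Use one definition of withdrawal of consent in the glossary and in 9.1.2, without adding a hurdle to withdrawal.
2. At withdrawal, record two answers separately: whether the patient refuses visits and contact, and whether the patient also refuses further data collection.
3. Where data collection is not refused and consent and local rules allow, take invasive ventilation and vital status through Day 29 from the hospital record without contact. Use them in the primary and 4-week fatality analyses in place of the default rules.
4. Limit the missing-data sentence in 9.1.2 to patients who refuse further data collection. The existing rules for early exit then apply to them and to patients whose record cannot be obtained.
5. Report by arm how many patients fall in each category, so that any imbalance is visible.

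Cost: protocol and consent wording that needs ethics approval, one extra eCRF disposition field, and record review at sites for a few patients. There are no new patient procedures and no change to the sample size.

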## Amendment 1 (01-Jun-2020)

### Amendment rationale

At the time of this amendment approximately 96 patients have been randomized and the study continues to screen patients.

This protocol amendment is primarily issued for the following reasons:

- A clarification on source data verification approaches was included to align with the EMA Guidance on the Management Of Clinical Trials During The COVID-19 (Coronavirus) Pandemic (Version 3, 28APR20).
- In addition, as requested by FDA, the inclusion criteria 2 was updated to allow patients  $\geq$  12 years of age to be included in the trial in the US only.

### Changes to the protocol

Inclusion criteria 2 was updated to include patients  $\geq$  12 years of age in the US only and the informed consent procedure in inclusion criteria 4 was updated in line with this. The [Protocol Summary](#) and [Section 3](#), [Section 5](#), [Section 5.1](#) and [Section 7](#), were updated with text regarding the modified inclusion criteria 2 and 4.

Clarification that all investigational medications being used in an investigational trial are prohibited was added to [Section 6.2.2](#).

[Table 8-1](#) was updated to clarify that assessments/procedures performed 0–24 hours prior to randomization could be included for screening purposes. This clarification was aligned throughout the document. The footnote was also updated to add guidance [REDACTED] and when samples should be taken. The text “if arterial blood gas was measured” was removed as a condition for measuring PaO2/FiO2 and this is reflected in [Section 8.3.2](#) also. Additional minor clarifications and editorial changes were made in the table.

[Section 8.3.1](#) was updated to add clarification on the timing of assessing the 9-point ordinal scale during the study and on Day 29/discharge.

In [Section 8.4.1.2](#), triglycerides was removed from the listed assessments in the chemistry panel, as these are not required.

[REDACTED]

[REDACTED]

[Section 10.1.4](#) was updated to clarify the reporting of enrolled pregnant patients to Novartis.

A clarification on source data verification approaches was added to [Section 11.3](#) to align with the EMA Guidance on the Management Of Clinical Trials During The COVID-19 (Coronavirus) Pandemic (Version 3, 28APR20).

[REDACTED]

Other minor edits have been made to further optimize the clinical trial protocol. Typographical errors have been corrected to increase clarity and consistency of the text.

### **IRBs/IECs**

A copy of this amended protocol will be sent to the Institutional Review Board (IRBs)/Independent Ethics Committee (IECs) and Health Authorities.

The changes described in this amended protocol require IRB/IEC and Health Authority approval according to local regulations prior to implementation.

The changes herein affect the Informed Consent. Sites are required to update and submit for approval a revised Informed Consent that takes into account the changes described in this protocol amendment.

The changes herein do NOT affect the trial specific model ICF. The US-specific protocol change to include patient's  $\geq 12$  years of age in the trial requires the addition of parent/guardian consent and adolescent assent.

